#### 1. Aim of study

The aim of this study is to compare the mechanisms, tolerability and efficacy of two high doses of psilocybin versus a 6 week course of a leading antidepressant medication, escitalopram, in major depressive disorder (MDD). This will be a 2-arm, active comparator, double-blind randomised control trial in a total of 60 completing volunteers ('completing' measured by primary outcome measure).

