## 2.1.2. Escitalopram

Escitalopram is a highly selective serotonin reuptake inhibitor (SSRI) that was licensed in the US in 2002 as an approved treatment for major depressive disorder. It has since been prescribed to millions of people worldwide, becoming a gold-standard medication for depression. Meta-analyses have indicated that escitalopram is one of the best performing SSRIs in terms of tolerability and efficacy [77] and it is one of the most selective SSRIs [78].

Patients in condition 2 who receive an inactive dose of psilocybin (1mg) during the first dosing day, will subsequently receive 6 weeks of daily escitalopram. For the first 3 weeks they will receive 10mg-daily (1 capsule per day). After 3 weeks they will have a second 1mg psilocybin dosing day (without interrupting the daily escitalopram dosing schedule). After this, they will subsequently take 20mg of escitalopram daily (2 capsules per day) for three further weeks. The dose of 20mg is the recommended maximum dose for this commonly prescribed primary treatment for depression, and thus we would expect the patient's symptoms of depression to decrease. It would be expected that patients starting a course of SSRIs would report some improvements in depressive symptoms after even this relatively brief treatment period of 6 weeks [80, 81].

The dose of escitalopram can be lowered to 10mg from 20mg if patients appear not to be tolerating 20mg and ask to lower the dose or withdraw from the trial. This would be simple to implement as we would just instruct patients to take 1 capsule daily instead of 2. If, when the blind is broken at the 6 week endpoint, it transpires that the patient was actually in condition 1 and not in fact in the escitalopram condition, this would be logged.

We will be monitoring patients' response to escitalopram via weekly self-report measures, and measures of side effects. FDA guidelines report the following possible side-effects with escitalopram: headaches, dizziness, nausea, insomnia, dry mouth, impotence, decreased appetite, weight gain, vomiting, vivid dreams and a tingling sensation in arms, hands, feet and legs [79]. Insomnia and diarrhea are the most common side-effects, affecting 15% of individuals at 20mg [79].

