#### 2.4.1 Managing risks related to withdrawal from antidepressants

PSILODEP RCT – Study Protocol, Version 7, 11/07/2019

Serotonergic antidepressants are known to attenuate the acute psychological effects of psychedelics [8] and thus, we feel it is necessary that patients withdraw from these medications in order to experience the full effects of the 25mg dose of psilocybin. This washout component of the design is consistent with our recent pilot study, as this was done safely and effectively in that trial. Withdrawal symptoms and a worsening of depressive symptoms can occur with antidepressant-withdrawal [9]; thus, we will incorporate a number of contingency measures to reduce associated risks, namely:

1) Patients will be free to leave the study at any point and return to their treatment as usual if they, their mental-health care-giver or the study team feel this is the right course of action.

2) The study blind will be broken at 6-weeks after the initial dosing session (fig 1), enabling patients to return to pre-study treatment/s if they so choose.

3) Study clinicians will offer telephone contact to patients during the withdrawal period, if this is required.

It is important to note that since recruitment to this trial is not restricted to patients with treatment-resistant depression, potential volunteers may well be unmedicated at the time of study entry. Thus, we can anticipate that challenges relating to withdrawal from medication will be less than in our previous open-label trial in treatment-resistant depression. Even so, antidepressant medication withdrawal was managed safely and effectively in that trial and we foresee that the same will be true in this trial.

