# Visit 7 (time since first dosing session = 6 weeks/time since second dosing session = 3 weeks)

The final study visit will take place 6 weeks after the first dosing session. This visit will include a final MRI scan. Patients will arrive at 10am and be scanned at 11am. The scanning session will last for no longer than 90 minutes. After this, patients will be asked to complete some questionnaires and will take part in a structured interview in which they will be asked how they have felt today and the past 6 weeks. The HAM-D and MADRS assessments will be performed which enquire about depressive symptoms over the last week. A comprehensive side-effects questionnaire will also be completed, which asks about side-effects over a 6-week period [11]. A second ECG scan will also be conducted in order to ensure no effect of either drug on heart physiology and a repeat routine blood test will be done (see above for a complete list of tests). This visit will take approximately 5 hours in total. At the end of this visit, we will inform the patient of the condition they **were** enrolled in; thereby breaking the blind. Breaking the blind at this time point will enable us to assess treatment safety and efficacy for both conditions

and provide the patient with information on what they have received - which may then inform future decisions regarding treatment, e.g. whether or not they want to continue with escitalopram if they were in condition 2.

Study Timeline			
Date	Event	Main assessment/s	Approximate Duration
Visit 1	Screening	QIDS, HAM-D MADRS, ECG	5 hours
Visit 2	Scan 1	QIDS, HAM-D, MADRS, scan measures	5 hours
Visit 3	Dosing session 1 (DS1)	ASC, EDI, etc	8 hours
Visit 4	1-day post DS1	QIDS, interview	2-3 hours
Visit 5	Dosing session 2 (DS2)	ASC, EDI, etc	8 hours
Visit 6	1 day post DS2	QIDS, interview	2-3 hours
Visit 7	Final visit + scan 2 6-weeks post DS1	QIDS, HAM-D, MADRS interview, ECG, scan measures	5 hours

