## Less common (< 10%)

- 1) Frequent urination
- 2) Indigestion
- 3) Increased or decreased appetite
- 4) Taste alterations
- 5) Tremor (shaking)
- 6) Tingling in arms or legs
- 7) Weight changes
- 8) Influenza-like symptoms and pain in neck or shoulders
- 9) Serotonin syndrome
- 10) Suicidal thinking and behavior
- 11) Abnormal bleeding
- 12) Seizures
- 13) Manic episodes
- 14) Low sodium
- 15) Angle closure glaucoma

The MHRA recommends that escitalopram should not be used in patients with known QT interval prolongation (above 440ms in men and above 470ms in women) or in combination with other medicines known to prolong the QT interval. An ECG during the screening visit will ensure that such individuals will be excluded from the study. To prevent antidepressant discontinuation syndrome, gradual withdrawal from escitalopram will be managed by the study psychiatrist in consultation with the patient's GP/psychiatrist.

In the event of signs of cardiac arrhythmia (fluttering in chest, tachycardia, bradycardia, chest pain, shortness of breath, lightheadedness, etc), patients will be advised to contact us and their GP immediately and stop escitalopram dosing. In this case, we would schedule an extra visit and perform an extra ECG.

Additionally, the Summary of Product Characteristics (SmPC) for escitalopram [100] advises caution in patients with severely reduced renal function (CLCR less than 30 ml/min). We are aiming to recruit depressed patients who are otherwise physically healthy and will be excluding patients with severely reduced renal function as per exclusion criteria.

The SmPC for escitalopram [100] also raises cautions about its use in patients with hepatic impairment. In the case of mild or moderate hepatic impairment, dose reduction is necessary. For consistency, patients with any form of hepatic impairment will be excluded (see section 4.2.4). Liver Function Tests (LFTs) conducted in screening will provide the study medical doctor with the necessary information to make this assessment.

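### The comprehensive side-effects questionnaire, scheduled second ECG and repeat bloods sit at Visit 7 with no exit assessment, so they describe only patients who reach week 6

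*Protocol*

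**What the plan says.** Section 1 sets out to "compare the mechanisms, tolerability and efficacy of two high doses of psilocybin" against escitalopram, and section 1.1 predicts that the two conditions will differ in side effects.

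Under Visit 7, section 2.6 places three safety measurements six weeks after the first dosing session:
- the questionnaire: "A comprehensive side-effects questionnaire will also be completed, which asks about side-effects over a 6-week period";
- the ECG: "A second ECG scan will also be conducted in order to ensure no effect of either drug on heart physiology";
- the bloods: "a repeat routine blood test will be done".

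No other administration of that questionnaire is named. The only other post-dose ECG is conditional: 7.2.1 covers signs of arrhythmia and says "In this case, we would schedule an extra visit and perform an extra ECG".

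On leaving, 2.4.1 states: "Patients will be free to leave the study at any point and return to their treatment as usual". Section 4.2.4 lists withdrawal criteria and discussion with health professionals, but no measurement at exit. Section 5.2 allows withdrawal without a reason.

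Other safety information is also planned. Section 7.5 collects all adverse events from consent to the end of the study. Section 2.7 lists the PRSEXDQ-SALSEX, the OQuESA and the Barnes Akathisia Rating Scale among measures taken before and after treatment. Section 2.1.2 refers to monitoring that includes side-effect measures, without naming an instrument or a time.

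**The concern.** A patient who leaves because of a side effect does not answer the questionnaire that would have recorded it. The reason for the missing value is then the quantity being measured, and the questionnaire describes the patients who tolerated treatment well enough to stay. If one arm loses more patients this way, its questionnaire results look better than they should, on an outcome that the trial sets out to compare.

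The ECG and bloods have the same gap. A patient who leaves without signs of arrhythmia has no scheduled ECG after dosing.

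This is a matter for the protocol. A SAP can choose analysis sets and methods for missing data, but it cannot supply an assessment that was never made.

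**Working it through.** **No stated figure to reproduce.** The Protocol gives no dropout rate and no side-effect rate for this questionnaire. The check has two parts: what the schedule provides for a leaver, and an illustration of size.

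**1. What a patient who leaves before Visit 7 contributes**

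| Source | Stated timing | Available for an early leaver? |
|---|---|---|
| Side-effects questionnaire (2.6) | Visit 7 | No administration described |
| Scheduled second ECG (2.6) | Visit 7 | No; 7.2.1 adds one only for signs of arrhythmia |
| Repeat bloods (2.6) | Visit 7 | No |
| PRSEXDQ-SALSEX, OQuESA, Barnes scale (2.7) | Before and after treatment | No exit administration described |
| Unnamed side-effect measures (2.1.2) | Not stated | Cannot be determined |
| Adverse events (7.5) | Consent to end of study | Yes, for events before departure |

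**2. Size, with assumed numbers**

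Let n patients start an arm, x have a given side effect, and k of those x leave because of it.

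- Rate among all starters: x/n
- Rate seen at Visit 7: (x − k)/(n − k)
- Understatement: x/n − (x − k)/(n − k) = k(n − x)/[n(n − k)]

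I take n = 30. In the Protocol, 30 per condition is the target for completers, so using it for starters is an assumption. The values of x and k are also assumed.

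| x | All starters | Visit 7, k = 1 | Points lost | Visit 7, k = 3 | Points lost |
|---|---|---|---|---|---|
| 9 | 9/30 = 30.0% | 8/29 = 27.6% | 2.4 | 6/27 = 22.2% | 7.8 |
| 12 | 12/30 = 40.0% | 11/29 = 37.9% | 2.1 | 9/27 = 33.3% | 6.7 |
| 15 | 15/30 = 50.0% | 14/29 = 48.3% | 1.7 | 12/27 = 44.4% | 5.6 |

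Section 2.1.2 quotes 15% for insomnia and diarrhoea at 20 mg. Used only as an illustrative rate, the expected count is 30 × 0.15 = 4.5. One affected leaver gives 3.5/29 = 12.1%, and three give 1.5/27 = 5.6%.

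If 30 is read as completers and 33 start, 12/33 = 36.4% becomes 9/30 = 30.0%. The loss is 6.4 points, so this choice matters little.

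**3. Direction**

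The fall above follows from assuming that every leaver has the side effect. If three unaffected patients leave instead, for example through the deterioration criterion in 4.2.4, 12/30 = 40.0% becomes 12/27 = 44.4%, a rise of 4.4 points.

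The contrast between arms moves only as far as departures differ. With 12/30 affected in both arms and three affected leavers in one arm only, the questionnaire shows 33.3% against 40.0%. With three affected leavers in each arm it shows 33.3% in both: no false difference, but both rates too low.

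**The case against.** A reader might infer that patients who cannot tolerate treatment drop out of the tolerability comparison altogether and that the side-effect comparison will be reported wrongly. The Protocol does not support that.

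- Adverse events are collected in every patient (7.5), so an event before departure is within scope. Serious events have a form recording onset, severity and outcome, and 7.4 sets a causality scale. Visits 4 and 6 include structured interviews, and there is a call at one week.
- No section says that tolerability will be compared on the Visit 7 questionnaire alone, or only among those who attend. That choice commonly belongs to the SAP, which is not at hand.
- The questionnaire is not the only structured measure. The example in 1.1, sexual dysfunction, has its own scale in 2.7.
- It is tempting to read 2.1.2 as a forecast of withdrawals. The words "if patients appear not to be tolerating 20mg and ask to lower the dose or withdraw from the trial" give the condition under which the dose can be lowered, so the sentence offers an alternative to leaving. A patient who reduces or stops capsules but stays in the study can still attend Visit 7.
- The number of leavers is assumed, and the direction depends on who leaves.

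All of this stands, and it limits the point to particular instruments. It does not close the gap. Section 7.5 sets reporting routes and deadlines but no checklist or schedule for asking about side effects, so the adverse-event record cannot replace a leaver's missing questionnaire. The scales in 2.7 have no exit administration either, and 2.1.2 is too indefinite to fill the gap.

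**Conclusion.** The point holds for the Visit 7 instruments and no further. As scheduled, data from the comprehensive questionnaire, the planned second ECG and the repeat bloods will be limited to patients who reach week 6.

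In an arm of 30 with 9 to 15 affected patients, the questionnaire would understate the side-effect rate by 1.7 to 2.4 points if one affected patient leaves, and by 5.6 to 7.8 points if three do. This rests on three assumptions: 30 starters, the stated numbers of leavers, and all leavers having the side effect. The Protocol gives no dropout rate to test them, and the shift reverses if the leavers are unaffected. Bias between arms also needs unequal departure.

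This is a cheap improvement to data collection that is worth making. It is not evidence that the tolerability comparison as a whole is unsound.

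**What to change.** 1. In 2.6 and 4.2.4, state that every dosed patient who leaves before Visit 7 will be offered the same side-effects questionnaire remotely, on the survey platform already used for the QIDS, covering the time since the first dosing session.
2. Report adverse events and withdrawals by arm for all dosed patients beside the questionnaire results, with reasons where the patient gives them, since 5.2 does not require any.
3. Reconcile 2.1.2 with 2.6: name the side-effect measures meant in 2.1.2 and state when each is given.

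The cost is one existing questionnaire sent to those who leave early, plus a few lines of text. Some leavers will decline, and their recall period will be shorter than six weeks, so their answers should be identified as exit assessments. Extra in-person ECGs or bloods for leavers, and any rule counting a withdrawal as a side-effect case, are separate decisions and are not needed for this change. No change to dose, stopping or treatment rules is proposed.

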#### 2.7. Psychological outcome measures

Measures completed before and after treatment will include the following:

## • QIDS-16 (primary efficacy outcome measure) [12]

- o QIDS-16 (daily measure) [82]
- o BDI II (two-weekly measure) [13]
- o HAM-D [14]
- o MADRS [34]
- Spielberger's Trait Anxiety Inventory (STAI) Trait [15]
- Warwick-Edinburgh Mental Wellbeing Scale (WEMWBS) [16]
- Flourishing Scale (FS-8) [102]
- o Snaith Hamilton Anhedonia Pleasure Scale (SHAPS) [17]
- Life Orientation Test (LOT-R) [18]
- Meaning in Life Questionnaire (MLQ) [19]
- Brief Resilience Scale (BRS) [20]
- o Dysfunctional Attitudes Scale (DAS) [21]
- o 44-item Big Five Inventory [22]
- Peters 21-item delusional inventory (PDI) [23]
- EASE anomalous subjective experience [24]

- Ruminative Responses Scale (RRS) [25]
- White Bear Suppression Inventory (WBSI) [26]
- Barrett Impulsivity Scale (BIS) [27]
- o Brief Experiential Avoidance Questionnaire [28]
- Modified Tellegen Absoprtion Questionnaire (MODTAS) [29]
- o Scale To Assess the Therapeutic Relationship (STAR) [30]
- Credibility/Expectancy Questionnaire [31]
- Connectedness to Nature Scale (CNS) [32]
- Political Perspective Questionnaire (PPQ)
- Social Connectedness Scale (SCS) [33]
- o Bech-Rafaelsen Mania Rating Scale (MAS/MRS) [34]
- Revised Santa Clara brief compassion scale (5 items) (SCBCS) [35]
- o Gratitude Questionnaire (GQ-6) [36]
- Short Suggestibility Scale (SSS) [37]
- Self-esteem: Rosenberg Self-Esteem Scale [4-items] (RSE) [38]
- Universality subscale of the Spiritual Transcendence Scale (STS) [39]
- o Oxford Questionnaire on the Emotional Side-effects of Antidepressants (OQuESA) [40]
- Lauks Emotional Intensity Scale (LEIS) [41]
- The Suicidal Ideation Attributes Scale (SIDAS) [84]
- Sexual dysfunction (PRSEXDQ-SALSEX) [83]
- Selected items from Brief Index of Sexual Functioning for Women (BISF-W) [104]
- o 2-item Sexual Perceptions Questionnaire (SPQ, self-constructed)
- Barnes Akathisia Rating Scale (BARS) [85]
- Work Productivity and Activity Impairment Questionnaire (WPAI) [87]
- The Work and Social Adjustment Scale (WSAS) [88]
- o Self-constructed Connectedness Questionnaire
- Standard Assessment of Personality Abbreviated Scale (SAPAS) [96]
- Positive and Negative Syndrome Scale (PANSS) [97]
- o Mastery Insight Scale (MIS, taken from Therapeutic Realisations Scale [103])
- o Self-Reflection and Insight Scale (SRIS) [106]
- Psychological Insight Scale (PIS, self-constructed)
- Metaphysical Beliefs Questionnaire (MBQ, self-constructed)
- Spiritual Bypassing Scale (SBS, self-constructed)
- Adverse Childhood Experience Questionnaire (ACE) [105]
- Therapeutic Music Experience Questionnaire (TMEQ, self-constructed)
- Setting Questionnaire (SQ, self-constructed)
- Selected Items from the Absorption in Music Scale (AIMS revised)

- o Acceptance and Action Questionnaire (AAQ-II) [107]
- CompACT Questionnaire [108]

Although there are a large number of these measures, they are intentionally brief. It will take approximately 75 minutes to complete them. Patients will be encouraged to do this in two or more 'stints' and to take a break if/when they become tired and lose focus.

Measures completed just before treatment will include the:

- Spielberger's Trait Anxiety Inventory (STAI) State [15]
- The psychedelic predictor scale (self-constructed)
- The surrender scale (self-constructed)

## Behavioural tasks will include:

- Emotional processing battery [88]
- Cued autobiographical memory task (AMT) [44]
- Prediction of Future Life Events (POFLE) [45]
- Torrance Test of Creative Thinking (TTCT) [46]
- Emotional response to music [89]
- California Verbal Learning Test (CVLT) [90]
- Digit Symbol Substitution Test (DSST) [91]

The following scales will be used to measure subjective states during the dosing sessions to be filled out at the end of the dosing session:

- Ego Dissolution Inventory (EDI) [47]
- Mystical Experience Questionnaire (MEQ) [48]
- 11 Dimension Altered States of Consciousness Scale (11D ASC) [49]
- Psychotomimetic States Inventory (PSI) [50]
- Visual Analogue Scales (VAS)
- Geneva Emotional Music Scales (GEMS) [51]
- The Challenging Experience Questionnaire [52]
- The Imperial Emotional Breakthrough Inventory (EBI)
- Near-Death Experience (NDE) scale [53]
- o Ten Item Personality Inventory (TIPI) [88]

With prior consent, we will also send a patient's significant other a short questionnaire at baseline and at the 6-week end point to enquire how they perceive the patient's depression and whether they have noticed any changes in the patient's behaviour since the intervention.

#### 2.8. Scanning outcome measures

- o BOLD response to emotional faces (primary fMRI outcome measure)
- o Resting state blood oxygen level dependent (BOLD) signal scan
- Resting BOLD with music as hedonic stimulus
- Anatomical scans (T1 & T2)
- o Diffusion Tensor Imaging (DTI) scan

#### 3. Basic safety and scientific background

The LD50 of psilocybin in rats is 280mg/kg [54]; thus, in terms of toxicity, its margin of safety is very large. We intend to give no more than 25mg which equates to less than 0.3 mg/kg. Doses of 30mg and higher have been used in previous research with healthy volunteers and patients without serious adverse events [55; 56]. Common adverse events with high doses of psilocybin include sub-acute headaches which last for 1-2 days maximum, and acute anxiety, which subsides with psychological reassurance or as the acute drug effects subside [1]. Psilocybin has been given to several hundred patients and volunteers in modern studies. In a thorough review of dosing sessions in 110 healthy subjects, dysphoric experiences/bad trips were rare and dose-dependent. Moreover, there is no evidence of subsequent drug abuse, flashback phenomena or prolonged psychoses [57]. We observed no cases of persistent adverse effects of psilocybin in our recent trial of psilocybin for depression in 20 patients. Psilocybin is not habit forming in animals or humans [58] and none of the patients expressed craving for psilocybin.

Reports from the 1960s on the use of psilocybin in psychotherapy indicate clear benefits over harms [59]; however, these studies suffer from a lack of experimental control and standardised assessments. More recently, pilot studies have tested the efficacy of psilocybin in OCD [60] and anxiety related to terminal cancer [3]: In the former study, short-term reductions in compulsive symptoms were reported by all of the patients. In the latter study, trait anxiety was significantly decreased 1 and 3 months post session and depression scores were significantly decreased at 6 months. No clinically significant adverse events were observed in either study. In a large sample of healthy volunteers, orally administered high dose psilocybin induced mystical or spiritual-type experiences in over 60% of subjects [56]. 67% rated their experience as either the single most meaningful experience of their lives – or among the top five. In a

follow-up after 14 months, 64% of the sample maintained that the acute experience had led to a significant improvement in their sense of well-being or life satisfaction [61].

In the last four years, we have completed one pilot study [62], two fMRI studies [63] and one MEG study involving psilocybin [64], as well as a pilot study in treatment resistant depression (n = 20) [65]. We have carried out around 100 dosing sessions in total most with a dose equivalent to that proposed here and have seen no serious adverse events.

